### **2.2 Secondary Objective**

To evaluate the initial impact of the intervention. We expect the following for the experimental group:

- Infants will have enhanced self-regulation of energy intake (closer to estimated energy requirements) than the control group by T3.

## **3 INVESTIGATIONAL PLAN**

### **3.1 Study Design**

Two-group randomized repeated measures design with an intervention group and a control group of mother-infant dyads. For the intervention, we plan to teach mothers American Sign Language (ASL) signs indicative of hunger, thirst, and satiety, which they will in turn teach their preverbal infant. This training in ASL will be augmented with targeted information for mothers about infants' capacities to self-regulate energy intake in response to hunger and satiety and communicate those states with intention. Mothers also will be taught about expected development of infants' eating behaviors and nutritional requirements to support healthy growth. For the control group, dyads will participate in the same data collection as the intervention group and engage in their usual care provided by their health care provider, but they will not receive intervention content unless they elect to receive written lesson content once the study's data collection has ended and they have been debriefed.

#### **Study Phases:**

Screening: screening for eligibility and obtaining consent

Study Treatment: study intervention/experimental treatment from baseline visit (T1: age 4-9-months) monthly until 3-months post-baseline (T2: age 7-12-months)

Follow-up: 6-months post-baseline (T3: age 10-15-months)

### **3.2 Allocation to Treatment Groups and Blinding**

Randomization will be stratified by age group (for developmental differences; 4-5-months-old, 6-7-months-old, and 8-9-months old). Computerized randomization lists will be generated by study

statistician and will be administered by the project manager. Study personnel who code videos of feeding interactions will be blind to group status.

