## PROTOCOL SYNOPSIS

Study Title	Enhancing Caregiver-Infant Communication to Prevent Obesity
Funder	Eunice Kennedy Shriver National Institute of Child Health and Human Development
Clinical Phase	Stage 1 for Behavioral Intervention Development
Study Rationale	
Once obese as an infant, the relative risk of remaining obese appears to rise with increasing age. Thus, the early years of life have been posited as an important target period for obesity prevention. Widely viewed as a response to genetic, interpersonal, and environmental factors, obesity fundamentally reflects an imbalance between energy intake and expenditure. Self-regulation of energy intake aligned with physiologic need is essential to this balance. The process(es) by which infants begin to disassociate eating behavior from physiologic need is unclear, thus it is crucial to better understand predictors of individual differences in self-regulation of energy intake.
 
A chronic mismatch between a caregiver's feeding behavior and the infant's state (feeding in the absence of hunger and/or feeding beyond fullness), is thought to contribute to obesity by undermining the infant's capacity to self-regulate intake; the current proposal will be the first to examine the effects on autonomic regulation.

Study Objective(s)	
Primary Outcome
 
To evaluate the initial impact of the intervention. We expect the following for the experimental group:
 
Infants will have more optimal growth (weight-for-length Z scores closer to 50th %) than the control group by T3.
 
Secondary Outcome
 
To evaluate the initial impact of the intervention. We expect the following for the experimental group:
 

○ Infants will have enhanced self-regulation of energy intake (closer to estimated energy requirements) than the control group by T3.

 
Tertiary Outcomes
 
To evaluate the initial impact of the intervention. We expect the following for the experimental group:
 

○ A) Dyads will demonstrate (1) improvement in observed feeding responsiveness and (2) higher observed feeding responsiveness than the control group by T3 (6-months post-baseline).

○ B) Mothers will (1) perceive higher infant satiety responsiveness and (2) report more responsiveness

---

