## **4 STUDY PROCEDURES**

**4.1 Screening/Baseline Visit procedures:** Families will be recruited from a community sample through a variety of means, including email listservs, in-person interactions with study personnel, social media posting to local parenting groups, and publicly posted flyers. Those wishing to learn more about the study will contact our project manager, who will conduct screening and enrollment for those wishing to participate in the study.

**4.2 Intervention/Treatment procedures (by visits):** Intervention families will receive approximately 4 hours of ASL and development specific content related to language and feeding during home visits and phone calls. The initial in-home session with families will focus on teaching ASL signs indicative of hunger, thirst, and satiety. A video and placemat of mealtime signs will be left with families at the completion of the first visit. The remaining sessions, in-home over the next 3 months and by phone monthly thereafter for 6 months total, will focus on reinforcing ASL signing in addition to focused education on particular aspects of language development (receptive language preceding expressive language and increasing intentional communication), feeding development (such as hunger and fullness cues, fear of new foods, the importance of repeated food exposures, variations in intake from meal-to-meal, and the propensity to reject bitter tastes [many vegetables]), and appropriate portion sizes and variety for healthy growth.

In person visit lesson schedule (monthly from baseline at 4-9 months of age):

Visit 1 (baseline: T1): Signing with infants

Visit 2: Infant communication and responsive feeding

Visit 3: Nutrition, portion sizes, and neophobia

Visit 4 (T2): Infant intentionality

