## **10 DATA COLLECTION AND MANAGMENT**

Home visits will be scheduled to start about 45 minutes before a normal feeding time. Mothers will provide all food and will be encouraged to feed their children a typical meal. Upon arrival, four tripod-mounted digital video cameras will be set up; two in the typical place the baby is fed and two in the room

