where the rest of data collection will take place to minimize participant reactivity. After ASL and knowledge content delivery by the parent educator (experimental group only), participants will then prepare for cardiac data monitoring and video-recording. The initial period of training by the parent educator should allow some time for mother and child to adjust to the presence of study staff in their home and recover from any physiological arousal or reactivity in response to them. Then, an ambulatory electrocardiogram (ECG) monitor will be placed on mother's and infant's chests in order to record RSA patterns throughout the observation. This single channel ECG waveform recorder (Actiwave Cardio; Camntech) will be connected to two disposable ECG electrodes (ConMed Neonatal/Pediatric Huggables) placed below the sternum and on the left side of the body (connected to each other by a short lead). The Actiwave Cardio monitors are flat, lightweight (<8 g), and comfortable with high levels of intra- and inter-instrument reliability as well as good validity of measures. Interbeat interval (IBI) data will be monitored and recorded for R-wave detection (providing an estimate of the degree of vagal influence on heart rate). RA's will instruct mothers on how to place 2 electrodes onto her chest and her infant's chest. After a brief test of the signal strength, the infant's length and weight (in clean dry diaper only) will be measured in triplicate, using a calibrated length board and digital scale. Given the much shorter duration of our proposed monitoring (~1 hour), we feel confident in our ability to capture RSA data in both mother and infant. Then, mothers and infants will be given a 5-minute break to relax in order to give them time for de-escalation after physical measurements. Next, infants will listen to soothing music while seated in a baby seat (or other arrangement recommended by mother; for example, if infant is more comfortable and less likely to become distressed on a blanket or in a crib, we will do this instead) and mothers will read a neutral magazine (gardening) for a 4-min baseline measurement. Monitors will be worn for the entirety of the visit and feeding events will be marked within the time-stamped data. Video-recording will begin after intervention (or usual care) delivery, with mothers asked to wait at least 10 minutes after the video-recording begins before feeding their child. They can then feed their child whenever they feel it is appropriate. One camera will focus on the mother's facial expressions and movements and the second camera will focus on the infant's facial expressions and movements. As long as the infant is stationary during feeding (in mother's lap, a highchair, or booster seat), the infant's videographer will focus the camera at the beginning of the recording and then step away from the camera to minimize intrusiveness. Both videographers will swivel the camera and use the digital zoom to follow mother or child throughout the observation. From this position, the videographers can use the digital viewfinder and be out of view from the feeding room if possible. Video-recording will last until 2 minutes after the child's last bite of food. We are currently testing and refining these data collection protocols. All other self-report data from questionnaires other than NDSR will be entered in the field using Research Electronic Data Capture (REDCap) through UNC-Chapel Hill CTSA. Within a week of T1, T2, and T3, two 24-hour recalls (to account for day-to-day variation) will be collected using NDS-R software by telephone five to 10 days apart. Twenty-four-hour recalls provide intake during a specified period, are open-ended, can accommodate various foods or food combinations, do not require literacy and have a relatively low respondent burden.

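### The blinding promised for coders of the feeding videos is unreliable and unchecked, because the signs taught to one arm can be seen in the material being rated

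*Combined protocol and SAP*

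**What the plan says.** Section 3.2, repeated in Section 8, makes one statement about masking: "Study personnel who code videos of feeding interactions will be blind to group status". It does not say how. Section 10 mentions two research assistants who code video under supervised access, without saying whether they are separate from the staff who visit homes.

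The intervention is described in Sections 4.2 and 7: "The initial in-home session with families will focus on teaching ASL signs indicative of hunger, thirst, and satiety". Mothers then teach the signs to their infants. The same sections add: "A video and placemat of mealtime signs will be left with families at the completion of the first visit". Section 3.1 says of control dyads that "they will not receive intervention content unless they elect to receive written lesson content once the study's data collection has ended".

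Section 10 sets up four cameras, "two in the typical place the baby is fed", and says of the feeding recording: "One camera will focus on the mother's facial expressions and movements and the second camera will focus on the infant's facial expressions and movements". On order within the visit: "Video-recording will begin after intervention (or usual care) delivery". The lesson schedule in Section 4.2 places the signing lesson at Visit 1, which is T1.

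The synopsis lists observed responsiveness as tertiary outcome A, including "2) higher observed feeding responsiveness than the control group by T3". Section 5 measures it with the RCFCS at T1, T2 and T3.

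**The concern.** The behaviour that defines the intervention is performed in front of the camera whose footage is rated. A coder who has never been told the allocation may still infer it from a feeding sign or from a placemat in the picture. The better the intervention is taken up, the more often this can happen.

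The RCFCS is scored by people from video, and the blinding statement is the only protection that the plan gives it. If coders rate recognised intervention dyads a little more favourably, the error runs in the direction of the trial's hypothesis. The plan includes no step that would limit this or allow it to be detected afterwards: no rule on study materials in view, no masking of visit order, no record of coders' guesses, and no rule for how a sign counts towards the score.

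**Working it through.** **What the sections imply together.** Signs and placemat are given to one arm only (3.1, 4.2). Filming takes place where the baby is usually fed and follows the movements of both partners (10). So the rated footage can carry a marker of the arm. On timing, the T1 recording comes after the first signing lesson at the same visit, so signs can appear at T1. The placemat is left at the end of that visit, so it bears on T2 and T3 only, and only if it is in view.

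**Inputs from Section 6.4.** 32 dyads per group, one-sided .05, AR(1) correlation with rho = 0.9, hence a T1-to-T3 correlation of 0.9² = 0.81.

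**Assumptions, none of them in the documents.** No true effect; a rating bias of b (in SD) on intervention videos that the coder recognises; a recognised share q at T3; no bias at T1; no bias on control videos.

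**Standard errors of the group difference.**
- T3 only: √(2/32) = 0.25 SD.
- T1-to-T3 change: variance 2(1 − 0.81) = 0.38, so √(2 × 0.38/32) = 0.154 SD.
- With partial recognition, the intervention-arm variance gains b²q(1 − q), so the standard error is √([0.38 + 0.38 + b²q(1 − q)]/32).

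**Scale check against the plan's own figure.** For a true .4 SD difference, the change test has power Φ(0.4/0.154 − 1.645) = .83 (.82 by noncentral t), against a stated value above .86. Adjusting T3 for T1 (variance 1 − 0.81² = 0.344) gives .86 (.85 by noncentral t). The set-up is close enough for an illustration, and this point does not dispute the power figure.

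**False-positive rate** = 1 − Φ(1.645 − bq/SE). For the change test, noncentral t with 62 df gives the same two decimals.

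| Bias b | Change, q = 25% | Change, q = 50% | Change, q = 100% | T3 only, q = 100% |
|---|---|---|---|---|
| 0.1 SD | .07 | .09 | .16 | .11 |
| 0.2 SD | .09 | .16 | .36 | .20 |

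Both kinds of test matter, because Section 6.3 allows either a difference in slopes or group contrasts at each visit.

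**If bias is also present at T1.** In the change test the net shift is b(q at T3 − q at T1). With b = 0.2 SD, all T3 videos recognised and half of the T1 videos recognised, the net shift is 0.2 × (1 − 0.5) = 0.1 SD, and the rate falls from .36 to about .16. With equal recognition at T1 and T3 the bias cancels and the rate returns to .05. The simple T3 difference has no such cancellation.

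**The case against.** The strongest case on the other side has four parts.

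- **The statement can be literally true.** Coders can be kept from knowing the allocation. A reader might infer that the videos are in effect rated unblinded, but the documents do not support that. They do not show how many clips would contain a sign, and control families are not barred from signing on their own, so a sign is not proof of arm.
- **The timing weakens any growing-bias argument.** A reader might suppose that recognition starts only at T2, so that bias must build over time and mimic an intervention effect. Section 10 contradicts this: signs can appear at T1, and bias shared by T1 and T3 drops out of a change or slope test. This stands, and it makes the change figures upper values for a given bias and recognised share at T3.
- **The placemat may never be on film.** The plan says that it is left with families, not that it is on the table during recording. This stands.
- **The stakes are limited.** The outcome is tertiary in a Stage 1 study. Weight-for-length and energy intake do not come from video. Section 10 says that data collection procedures are still being refined, and filming begins after the lesson, which keeps the lesson itself off the recording. The RSA aim is an association, not a comparison of arms, and rating error tied to arm would not by itself create it. All of this limits the weight of the point.

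What remains is that the plan asserts a safeguard that its own filming procedure can defeat, with no means of knowing how often it does.

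**Conclusion.** The concern holds in this form: coder blinding is unreliable and unchecked, rather than certainly lost. The affected results are the tertiary RCFCS comparison and, less directly, the responsiveness measure in the exploratory RSA analysis. The primary and secondary outcomes are untouched by it.

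The size depends on two quantities that the documents do not give: the share of videos recognised and the rating bias on them. Over the assumed range of 0.1 to 0.2 SD, with recognition from 25% to 100% and none of the bias present at T1, the nominal .05 becomes about .07 to .36 for T1-to-T3 change. For the T3 difference with full recognition it becomes .11 to .20. These figures show sensitivity and do not predict what will happen. The change is worth making because it is cheap and it determines how far the RCFCS result can be trusted.

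**What to change.** 1. In Sections 3.2 and 8, replace the claim of blindness with wording such as: *coders will not be told group status; signing on video may reveal it*. State that the RCFCS result will be interpreted as partially masked.
2. In Section 10, give coders the clips in random order across dyads and visits, with date and visit labels removed.
3. Have coders record after each clip whether a sign or study material was seen, and their guess of arm. Report both beside the RCFCS result.
4. Optionally, keep study materials out of camera view where this does not disturb the meal. This step is more debatable, since mothers are encouraged to feed a typical meal.

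**Cost.** A randomised coding list, a short extra item per clip and a weaker blinding claim. Randomisation, sample size and the primary analysis do not change. Masking stays incomplete: signs made on camera cannot be hidden, and the infant's visible age remains a cue to the visit.

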### **3.3 Study Duration, Enrollment and Number of Subjects**

We plan for 80 parent-infant dyads (160 subjects) randomized to invention (40 dyads) or control (usual care; 40 dyads). Length of participation will be 6-6.5 months and planned study duration is 2 years.

### **3.4 Study Population**

#### **Inclusion Criteria**

1. Subjects age 3 months to 50 years.
2. Mothers must be able to read, understand, and speak English or Spanish and be willing to be randomized and participate in data collection. Those who are randomized into the experimental group must also be willing to learn ASL specific to communication of hunger, thirst, and fullness.

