#### **Exclusion Criteria**

1. Dyads will be excluded if infants:
  - a. were born more than 6 weeks earlier than their estimated due date,
  - b. have any developmental delays or disabilities that make it difficult for them to eat, drink, or communicate,
  - c. attend regular daycare,
  - d. or will be younger than 4 months or older than 9 months at the time of the first ASL training.

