All families will be offered \$25, \$30, and \$35 at T1, T2, and T3 data collections, respectively. At the end of the study, control families will have the opportunity at the end of the 6-month study period to learn about what educational content was offered to the Experimental Group and study personnel will provide a booklet of this content to them and an ASL Signs of Feeding placemat if they wish. If subjects withdraw or are withdrawn from the study prior to arrival of the study personnel at their home for data collection, then no monetary incentive will be offered. If participating parent or infant withdraws or is withdrawn from the study once data collection has been initiated in their home, they will be offered one half of the possible monetary incentive amount for that visit for their attempt to participate. All subjects will be thanked for their interest and participation regardless of whether they complete all data collections.

See section 5 below for data collected at each visit.

- 4.3 Follow-up procedures (by visits):** Within a week of T1, T2, and T3 (6-months post-baseline), two 24-hour dietary recalls (to account for day-to-day variation) will be collected using NDS-R software by telephone five to 10 days apart. Intervention participants will also be contacted by the project manager with 48-hours of in-home study visits (1-4 above) to assess whether relevant intervention content was delivered.
- 4.4 Unscheduled visits:** N/A
- 4.5 Concomitant Medication documentation:** N/A
- 4.6 Rescue medication administration (if applicable):** N/A
- 4.7 Subject Completion/ Withdrawal procedures:** Subjects will complete the study at the completion of data collection associated with T3. At the end of the in-home data-collection visit at T3, all participants will be asked to provide feedback on their experiences with recruitment, interactions with study personnel, data collection, and anything else they would like to share about the study. If a participating dyad chooses to withdraw from the study or we are unable to reach them after three attempts for scheduling of visits or data collection, they will be withdrawn from the study, but their data will be kept for analysis. All subjects will be thanked for their interest and participation regardless of whether they complete all data collections.

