### **6.3 Statistical Methods**

Descriptive statistics will be calculated for each measure (see Aims 2 & 3 in Table of Measures, Section 5) at each time point by group. All analyses will be conducted using an intention-to-treat approach.

Preliminary analyses will be conducted to determine whether, despite randomization, the intervention and control groups exhibit a random imbalance at baseline on any measured variable. If important imbalances are found, the corresponding variable will be considered as a covariate in subsequent models to statistically correct for the imbalance. To evaluate the initial impact of the intervention longitudinally for each maternal and infant outcome listed above as primary, secondary, and the first two tertiary outcomes (i.e., more optimal growth, indicators of enhanced self-regulation of energy intake [NDS-R data compared to age- and sex-specific estimated energy requirements], reported infant feeding behavior and maternal feeding behaviors/beliefs, and observed dyadic feeding responsiveness), we will fit separate linear mixed-effects models. These could include a random coefficients model to examine the linear trajectories of the group-specific means across all available time points using the actually observed timing. The initial impact of the intervention will be formally assessed through a statistical hypothesis test of model parameter representing the difference in these slopes. More specifically, these models will include terms for the intervention group (as an indicator variable), actual time of data collection (as continuous weeks from baseline), and their interaction. An alternative modeling strategy would be to utilize mixed-effects model in a repeated measures context to examine the trajectories of the group-specific means across all available time points using the visit timepoint; these models will include terms for the intervention group (as an indicator variable), visit timepoint (as one or more indicators to reflect this categorical variable), and their interaction term(s). In this scenario, the initial impact of the intervention will be formally assessed through a statistical hypothesis test of linear contrasts of model parameters representing the between-group difference at each timepoint. Covariates identified above to correct for imbalance will be considered for inclusion in these models, as well as the factors stratified in the randomization, and the models will account for the repeated measures correlation structure. Statistical contrasts will also be constructed to estimate and test the changes over time separately for each intervention group. As useful information for planning subsequent studies, effect sizes for each measure will be calculated for each follow-up time point as the ratio of the mean difference between the intervention and the control groups to its standard deviation, as well as the producing the estimated correlation matrices across the repeated measures.

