## **9 SAFETY MANAGEMENT**

Study visit confirmation will occur prior to study visits and assessment of self-reported health of parent and infant will be conducted prior to data collection. Study personnel will be on-site in subjects' homes for the duration of data collection and will monitor the response of subjects during data collection. Should any concerns arise during data collection, they will be addressed immediately by study personnel and the PI and Co-I will be notified as soon as possible if they are not on site. Though unlikely, should any concerns arise after data collection, subjects will be given the PI's contact information to share their concerns and the PI will address concerns directly or through appropriate referrals. Any concerns that arise over the course of the study will be recorded and aggregated as part of the feasibility data and shared with the research team and the IRB as necessary.

We do not anticipate that any questions, anthropometric measurements, observations, or collection of cardiac data will cause discomfort or embarrassment, but mothers may stop interviews at any time, tell us that they do not wish to answer a question, refuse to allow infant measurement, stop an observation, or refuse collection of cardiac data at any time. We will respect their wishes. We will also let parents/primary caregivers know the following: "In addition, there may be uncommon or previously unknown risks that might occur. You should report any problems to the researchers. We are mandated to report any instances of child abuse."

Thus, individual subjects may electively withdraw from the study or the PI may withdraw an individual subject, or in this case mother-infant dyad, if they fail or are unable to comply with study procedures.

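### An ASL-willingness criterion worded for the experimental arm only, and withdrawal rules that missed lesson visits can trigger, risk differential missing T3 data

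*Combined protocol and SAP*

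**What the plan says.** **Eligibility.** The second inclusion criterion in section 3.4 (same text in the synopsis) first requires every mother to accept randomisation and data collection. It then adds: "Those who are randomized into the experimental group must also be willing to learn ASL specific to communication of hunger, thirst, and fullness". The age exclusion removes infants who "will be younger than 4 months or older than 9 months at the time of the first ASL training". Section 3.1 says of controls that "they will not receive intervention content unless they elect to receive written lesson content once the study's data collection has ended".

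**Withdrawal.** Under section 4.7, if "we are unable to reach them after three attempts for scheduling of visits or data collection, they will be withdrawn from the study". The same sentence covers dyads that choose to withdraw, and ends by saying that the data are kept for analysis. Section 9 adds that "the PI may withdraw an individual subject, or in this case mother-infant dyad, if they fail or are unable to comply with study procedures". Neither section describes measurement after withdrawal.

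**Contacts.** Section 4.2 gives experimental dyads four monthly in-home lessons. Visit 1 coincides with T1 and Visit 4 with T2; Visits 2 and 3 are lessons only. Monthly phone sessions follow. Controls have T1, T2 and T3.

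**Analysis.** Section 6.3 states: "All analyses will be conducted using an intention-to-treat approach". It does not define the analysis set. Its models use all available time points. Section 6.4 assumes a single 20% attrition rate for both arms.

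**The concern.** Eligibility should be settled before allocation and in the same way for everyone. A criterion that binds only after assignment to one arm allows less willing mothers to leave that arm while their counterparts stay among the controls. The documents do not say when randomisation falls relative to telephone or written consent. Section 10 places lesson content before measurement at the visit, so allocation must be known before the T1 measurements.

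The withdrawal rules use the same words for both arms, but the arms are not equally exposed to them. A control mother who is hard to reach between T1 and T2 triggers nothing, because nothing is due. An experimental mother who is equally hard to reach can fail the three-attempt rule over Visit 2 or 3, leave the study, and never be approached for T3.

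Section 6.1 makes T3 the primary endpoint. If its missingness depends on arm and on engagement, part of any T3 difference could reflect who was measured. A mixed model corrects for this only to the extent that the observed data explain the missingness.

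**Working it through.** **The plan's own figures.** 40 x (1 - 0.20) = 32 per group, as section 6.4 states. That section claims power above 0.86 for 0.4 SD at one-sided 0.05. The slope contrast as described gives about 0.83: variance 2(1 - 0.81) = 0.38, SE = sqrt(0.38 x 2/32). That shortfall is a separate matter and does not affect this point. What matters here is the implied T1-T3 correlation, 0.9 x 0.9 = 0.81.

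**Occasions after T1 on which a home visit must be scheduled.**
- Control: T2 and T3, so k = 2.
- Experimental: Visit 2, Visit 3, T2 (Visit 4) and T3, so k = 4.

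**Loss under the three-attempt rule.** The chance p of failing per occasion is an assumption; the documents give none. With independent occasions, loss = 1 - (1 - p)^k.

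| p | Control, k = 2 | Experimental, k = 4 | Excess f |
|---|---|---|---|
| 2% | 4.0% | 7.8% | 3.8 points |
| 4% | 7.8% | 15.1% | 7.2 points |
| 5% | 9.8% | 18.5% | 8.8 points |

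Of 40 dyads, the excess is about 1.5 to 3.5. Both arms stay within the 20% allowance, so the issue is imbalance and not total loss. Reduced numbers alone cost little: 28 v 32 dyads gives power 0.81 by the same calculation.

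**Bias.** Let g be the difference between retained and lost dyads in outcome SDs, assumed equal in both arms.

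- *Lost dyads differ by a stable level.* Their T1 values stay in the model, which predicts 0.81 of the difference at T3. The remainder is (1 - 0.81) x f x g = 0.19 x f x g. For f = 3.8 to 8.8 points and g = 0.5 to 1, this is 0.004 to 0.017 SD.
- *Lost dyads differ in change from baseline.* T1 gives no correction, so bias = f x g. For g = 0.5 this is 0.019 to 0.044 SD; for g = 1 it is 0.038 to 0.088 SD. The SD of T3-T1 change is sqrt(0.38) = 0.62, so g = 0.5 is already 0.8 SDs of change and g = 1 is 1.6.

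**Effect on the test.** With no true effect and 32 controls, f = 5% and g = 0.5 in change gives a bias of 0.025 SD and raises one-sided type I error from 0.05 to about 0.07. With f = 10% it is 0.05 SD and about 0.09.

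**Willingness criterion.** No refusal rate is given. A mother removed at Visit 1 before measurement would have no T1 value, so f x g would apply without the 0.19 factor. Two of 40 (5%) at g = 0.5 gives 0.025 SD. The documents do not say that such a mother would be removed.

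**The case against.** The strongest reply is that the plan already contains the right intentions. It commits to intention-to-treat, models all available time points, expects incomplete data and keeps withdrawn dyads' data. A reader might infer that the intention-to-treat comparison is lost; the documents do not support that, because leaving follow-up is not exclusion from analysis. What stands is narrower: data that were never sought cannot be kept, the analysis set is undefined, and the data-kept sentence does not mention PI withdrawals.

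The willingness sentence sits beside the requirement to accept randomisation and may be meant as a screening question about what a mother would do if allocated. That is plausible, but no passage puts the question to all mothers before allocation.

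A reader might also infer an age exclusion that operates in one arm only. That is strained. The first ASL session is the T1 visit (4.2), section 3.1 gives T1 age as 4-9 months without restricting it to one arm, and randomisation is stratified by age bands covering 4-9 months (3.2). Only a wording point remains.

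The withdrawal rules are not confined to one arm, and PI withdrawal is discretionary. Lesson phone calls are not clearly visits or data collection, so counting them as triggers, which would give experimental losses well above 20%, goes beyond the text. Unreachability probably clusters within families, so the independence formula tends to overstate the gap.

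**Conclusion.** The point holds as a risk of differential missing T3 data. One criterion is worded to bind only after allocation to the experimental arm. Two withdrawal rules have more occasions to operate there, with no follow-up afterwards.

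The size cannot be derived from the documents. At an assumed 2-5% per home-visit occasion, with independent occasions, loss is about 4-10% in controls and 8-19% in the experimental arm. The resulting bias is probably a few hundredths of an SD against the 0.4 SD target. It approaches 0.1 SD only if the lost dyads differ very strongly in change from baseline. The direction is not fixed by the text; it would favour the intervention if the mothers lost would have done worse.

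A reader might infer removal of 10-20% from one arm alone, with correspondingly larger bias. The rules do not imply that: controls are lost under them too, and retained T1 data absorb most of any stable difference. The change is still worth making because it is cheap and the fault cannot be repaired after data collection.

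**What to change.** 1. In 3.4 and the synopsis, ask every mother before randomisation whether she is willing to learn ASL if allocated to it.
2. As a minor wording point, date the age limit to the T1 visit for both arms.
3. In 4.7 and 9, separate stopping lessons from leaving the study. A missed or declined lesson ends lessons only.
4. Apply the three-attempt rule only to the T1, T2 and T3 data-collection visits, identically in both arms. Attempt T2 and T3 for all randomised dyads unless consent is withdrawn; a dyad missed at T2 is still approached for T3.
5. In 6.3, define the intention-to-treat set as all randomised dyads, analysed as allocated. Extend the data-kept statement to PI withdrawals.

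The cost is a few sentences, plus some extra contact attempts and T3 visits to poorly engaged families within the planned 80 dyads. Following dyads that stop lessons can dilute the observed effect. If 5-10% gained nothing, 0.4 SD becomes 0.38-0.36 SD, and power at 32 per arm falls from about 0.83 to 0.79-0.76. That is the effect an intention-to-treat analysis is meant to estimate, and better retention offsets some of the loss.
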